4.3.2 Electrocardiograms (ECG)

- Absolute and change from baseline values at Week 24, and Week 48
- Post-baseline abnormalities defined by the below categories:
 - Absolute QTcF (QT interval corrected using Fridericia's formula) prolongation
 - >450 msec
 - >480 msec
 - >500 msec
 - Change from baseline in QTcF Interval at Week 24, and Week 48
 - >30 msec
 - >60 msec

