 - k) History of weight gain/loss $\geq 10\%$ of body weight within 6 months (26 weeks) prior to or during the Screening Period
 - l) Uncontrolled hypertension, as defined by systolic blood pressure (SBP) > 160 and/or diastolic blood pressure (DBP) > 100 during Screening, unless discussed with medical monitor. Blood pressure may be rechecked as clinically indicated
 - m) QT interval corrected using Fridericia's formula (QTcF) > 480 msec on 12-lead ECG during Screening, confirmed by repeat ECG 30-60 minutes after the initial ECG
 - n) Any acute or chronic cardiovascular condition (e.g., ischemic heart disease, congestive heart failure) considered clinically significant by the investigator
 - o) Known immunocompromised status, including but not limited to, individuals who have undergone organ transplantation, who are known to be positive for human immunodeficiency virus, or who have recurrent or chronic systemic bacterial, fungal, viral or protozoal infections
 - p) Major episode of infection requiring hospitalization within 4 weeks prior to or during the Screening Period
 - q) Inability to tolerate SC medication
 - r) Inability to tolerate venipuncture
 - s) Women who are breastfeeding
4. Prior and concomitant therapy
- a) Participants who have taken systemic corticosteroids at a dose exceeding 20 mg/day prednisone or equivalent for more than 7 consecutive days at any time within 3 months (12 weeks) prior to or during the Screening Period
 - b) Inability to comply with restrictions and prohibited treatments
 - c) Prior exposure to BMS-986036 or other FGF21 analogs
 - d) Other investigational agents must be discontinued at least 4 weeks or 5 half-lives before the first dose of study medication, whichever is longer
5. Physical and laboratory test findings
- a) Evidence of organ dysfunction or any clinically significant deviation from normal in physical examination, vital signs, or clinical laboratory determinations beyond what is consistent with the target population
 - b) ALT value $> 5 \times$ the upper limit of normal (ULN) as defined by the central laboratory
 - c) AST value $> 5 \times$ ULN as defined by the central laboratory
 - d) Total bilirubin > 1.5 mg/dL (unless the participant has a documented diagnosis of Gilbert's syndrome)
 - e) Serum albumin < 3.5 g/ dL
 - f) Platelet count $< 100 \times 10^3/\mu\text{L}$
 - g) International normalized ratio (INR) > 1.4 , unless due to therapeutic anticoagulation

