8.5.3.5 Electrocardiograms

Twelve-lead ECGs should be collected at similar times during Baseline and on-treatment visits. ECGs may be collected at any time prior to study medication dosing or PK sample collection. ECGs should be recorded after the participant has been supine for at least 5 minutes. ECG parameters, including QTcF, will be collected on the eCRF.

If a participant has a QTcF > 480 msec during the Screening Period, it should be confirmed by repeat ECG 30-60 minutes after the initial ECG. If the QTcF is confirmed to be > 480 msec, the participant should not be allowed to participate in the study.

If a participant has a QTcF > 480 msec at an on-treatment visit, it should be confirmed by repeat ECG 30-60 minutes after the initial ECG. If the QTcF is confirmed to be > 480 msec, the medical monitor should be contacted.

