6.2.3 ECGs, Vital Signs, and Physical Examinations

Based on the safety population, vital sign and 12-lead ECG parameters will be summarized by visit, treatment group, and pooled BMS-986036. All vital signs and ECG results will be listed.

ECG results will be summarized for continuous variables and will be presented for the absolute result and change from baseline. QTcF (QT interval corrected using Fridericia's formula) values will be presented with the implementation of corrections (i.e., Fridericia's) as defined in ICH Guidelines E14 by the following categories:

Absolute QTcF interval prolongation:

- o QTcF interval > 450ms
- o QTcF interval > 480ms
- o QTcF interval > 500ms

Change from baseline in QTcF interval:

- o QTcF interval increases from baseline >30ms
- o QTcF interval increases from baseline >60ms.

Physical examination results and other safety data will be listed.

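### The QTcF >450 msec count has no baseline condition although entry is allowed up to 480 msec, so that one row mixes pre-existing with new values (minor)

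*SAP*

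**What the plan says.** SAP 4.3.2 places two sets of QTcF categories under "Post-baseline abnormalities defined by the below categories".

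- The first set is "Absolute QTcF (QT interval corrected using Fridericia's formula) prolongation", with cut-offs of 450, 480 and 500 msec. It carries no baseline condition and no visit restriction.
- The second set is "Change from baseline in QTcF Interval at Week 24, and Week 48", with cut-offs of 30 and 60 msec.

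SAP 6.2.3 repeats both sets, for example "QTcF interval > 450ms" and "QTcF interval increases from baseline >30ms". It names no weeks for either, and adds continuous summaries of the absolute value and of the change from baseline.

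On eligibility, Protocol 8.3.2 excludes a screening QTcF above 480 msec only when it is "confirmed by repeat ECG 30-60 minutes after the initial ECG". Protocol 8.5.3.5 agrees: "If the QTcF is confirmed to be > 480 msec, the participant should not be allowed to participate in the study". SAP 8.1 takes as baseline the last value before dosing on Day 1, falling back on screening if Day 1 is missing.

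**The concern.** The lowest cut-off lies 30 msec inside the eligible range. A participant with a stable QTcF between 451 and 480 msec is reported as having an abnormality after baseline although nothing has changed. The >450 rate in each arm is therefore part baseline status and part new onset, and a reader of the table cannot tell how much is which.

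The SAP is usually more careful. Treatment-emergent adverse events (SAP 8.4) must first occur or worsen after the first dose. Most laboratory cut-offs in SAP 4.3.5 sit at or beyond the entry limit:

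- albumin below 2.8 g/dL, where entry bars below 3.5;
- platelets below 75, where entry bars below 100;
- triglycerides, eGFR and glucose at the same limits as at entry.

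The ALT/AST row at 3 times the upper limit of normal shares the QTcF problem, since entry allows up to 5 times.

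What is at stake is how readable one descriptive safety row is, with about 49 participants per arm. No test, sample size or efficacy result depends on it.

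**Working it through.** **Inputs.** From the documents: the cut-offs (SAP 4.3.2, 6.2.3), the 480 msec entry limit (Protocol 8.3.2, 8.5.3.5) and about 49 participants per arm (Protocol 6.2). Neither document gives a QTcF rate, spread or baseline prevalence, so there is no figure of the plan's own to reproduce. Everything below on size rests on assumed values.

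**Who lands in the >450 row.** Three illustrative participants:

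| Baseline | Post-baseline | In >450 row | In >30 msec row |
|---|---|---|---|
| 470 | 470 | yes | no |
| 440 | 465 | yes | no (rise of 25) |
| 440 | 475 | yes | yes (rise of 35) |

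The first is unchanged and the second is a new crossing, yet they fall in the same cells. The change rows do not separate them.

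**Size in a simple model.** Let b be the share with baseline above 450, s the probability that such a participant is above 450 again, and q the new-onset rate in the rest. The displayed rate is b·s + (1−b)·q. Assume s = 0.8, with q = 2% on placebo and 6% on active (true ratio 3.0, true difference 4.0 points).

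| b | Placebo | Active | Ratio | Difference (points) | Carried over per arm (49·b·s) |
|---|---|---|---|---|---|
| 5% | 4.0 + 1.9 = 5.9% | 4.0 + 5.7 = 9.7% | 1.6 | 3.8 | 2.0 |
| 10% | 8.0 + 1.8 = 9.8% | 8.0 + 5.4 = 13.4% | 1.4 | 3.6 | 3.9 |
| 15% | 12.0 + 1.7 = 13.7% | 12.0 + 5.1 = 17.1% | 1.25 | 3.4 | 5.9 |

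The difference shrinks only by the factor (1−b).

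**Noise.** At b = 10% the carried-over count per arm has mean 49 × 0.08 = 3.9 and SD √(49 × 0.08 × 0.92) = 1.9. The difference between two arms has SD 1.9 × √2 = 2.7. The assumed drug excess is 49 × 0.90 × 0.04 = 1.8 participants. Chance imbalance in baseline status can exceed it.

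**Wider assumptions.** Ranges over b = 2–20% and s = 0.5–1.0:

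| New onset, placebo v active | Placebo count that is pre-existing | Ratio: true → displayed | Difference in points: true → displayed |
|---|---|---|---|
| 3% v 10% | 25–89% | 3.33 → 2.74–1.25 | 7.0 → 6.9–5.6 |
| 5% v 15% | 17–83% | 3.00 → 2.66–1.33 | 10.0 → 9.8–8.0 |

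**Relaxing equal persistence.** Using the same s in both arms assumes no drug effect in those who start above 450. A simulation without that restriction used a true mean of 420 msec, between-subject SD 20, within-subject SD 12 and measured baseline at most 480. It puts 9.5% above 450 at baseline. A 10 msec drug shift then gives:

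| Row | No shift | 10 msec shift | Ratio | Difference (points) |
|---|---|---|---|---|
| >450, any baseline | 9.5% | 19.2% | 2.0 | 9.7 |
| >450, baseline ≤450 | 5.5% | 13.8% | 2.5 | 8.3 |
| Increase >30 msec | 3.9% | 12.0% | 3.1 | 8.1 |

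The ratio is again lower without the condition, but the absolute difference is larger.

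**ECG visits.** Protocol Table 2 schedules ECGs on Day 1, Week 24, Week 48 and at ET. For a participant who stops before Week 24, ET is the only scheduled post-baseline ECG. In SAP 4.3.2 the Week 24 and Week 48 limit sits on the continuous line and the change-from-baseline QTcF line, not on the absolute rows. SAP 8.1 keeps unscheduled values out of the descriptive statistics except as baseline, so they do not fill the gap. The bone density endpoint in SAP 4.3.6 does name ET.

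**The case against.** The strongest reply is that the QTcF assessment does not rest on this row. The >30 and >60 msec categories and the continuous change are in the same sections and do not count a stable value as an event. Randomization balances baseline status on average. The SAP plans no ratio and no test for ECG data, and the displayed difference hardly moves. All ECG results are listed, and Protocol 8.5.3.1 requires significant ECG worsening to be recorded as an adverse event. QT prolongation is not an event of special interest. Table shells are in a separate document (SAP Appendix 2), so a shift table may already be planned. SAP 6.2.3 also cites ICH E14, though the sentence attaches it to the correction formula and states no baseline rule.

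Most of this stands, and it limits the point to one row. It does not make that row interpretable: listings allow case-by-case review but give no per-arm new-onset rate, and balance on average is weak protection at 49 per arm.

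Two stronger readings are tempting. A reader might infer that the plan dilutes any QTcF signal. The documents do not support that, because the change-based summaries are untouched and the absolute difference can even be larger without the condition. A reader might also infer that early stoppers drop out of all the QTcF counts. The absolute rows carry no visit limit and SAP 6.2.3 is unrestricted, so the gap is confined to two lines of SAP 4.3.2.

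**Conclusion.** The point holds, at minor severity. The >450 msec row counts pre-existing 451–480 msec values as abnormalities. This inflates the rate in every arm, lowers the ratio to placebo and adds noise. The >480 and >500 rows are largely, though not fully, protected: exclusion needs a confirmed screening value, whereas baseline is the Day 1 value. The missing condition, the eligible range and the ET wording are read directly from the documents. The size is not: the baseline share, persistence, onset rates and simulated spread are all assumptions, and a low share of participants above 450 at entry would make the effect small.

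**What to change.** In SAP 4.3.2 and 6.2.3, keep the unconditional categories if wanted, labelled as such. Add one of the following:

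- a new-onset count for each absolute category among participants at or below that cut-off at baseline; or
- a shift table of baseline by worst post-baseline QTcF (≤450, 451–480, 481–500, >500 msec).

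Separately, in SAP 4.3.2 add ET to the continuous line and the change-from-baseline QTcF line, to match Protocol Table 2 and the unrestricted wording of SAP 6.2.3.

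Both changes use ECGs already scheduled. The cost is a few words of SAP text, one table, and smaller denominators for the new-onset counts: at the >450 cut-off about 42 to 47 of 49 per arm if 5–15% start above 450 (49 × 0.85 = 41.7; 49 × 0.95 = 46.6).

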4.3.3 Vital Signs

- Absolute and change from baseline values at each visit

4.3.4 Physical Examinations

Full or abbreviated physical examinations will be conducted at each visit through Week 52/PTFU.

4.3.5 Clinical Laboratory Parameters

- Absolute and change from baseline values at each visit through Week 52/PTFU
- Potential hepatotoxicity by time point
 - Aspartate aminotransferase (AST) or alanine aminotransferase (ALT) > 3 x upper limit of normal (ULN) or > 5 x ULN
 - Total Bilirubin > 2 x ULN
 - (AST or ALT) >3 x ULN and Total Bilirubin > 2 x ULN

Sponsor: Bristol-Myers Squibb

Protocol no: MB130-068

- Post-baseline abnormalities defined by the below categories:
 - Serum albumin < 2.8 g/dL
 - Platelet count < 75 x 10³/ µL
 - Fasting plasma glucose <60 mg/dL or >350 mg/dL
 - Fasting triglycerides > 500 mg/dL
 - Estimated glomerular filtration rate (eGFR) < 30 mL/min/1.73 m²

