BMS-986036 was also studied in two Phase 2 studies. **Study MB130002** was a randomized, double-blind, placebo-controlled, parallel-group, multiple-dose study in obese participants with type 2 diabetes mellitus (T2DM). Over 90% of participants had evidence of underlying fatty liver, based upon the fatty liver index. In this study, participants self-administered BMS-986036 or placebo, SC, for 12 weeks according to one of the following dosing regimens: BMS-986036 (1, 5, or 20 mg QD), BMS-986036 (20 mg QW), or placebo (QD). A total of 96 participants received at least 1 dose of BMS-986036. BMS-986036 treatment improved insulin sensitivity, adiponectin, fasting TGs, LDL cholesterol, HDL cholesterol, apolipoprotein C3, and N-terminal type 3 collagen propeptide (PRO-C3) (a biomarker for type 3 collagen formation, and hence, potentially, fibrosis). Dose-dependent increases in adiponectin were observed in all BMS-986036 dose groups. Meaningful changes in body weight were not observed.¹⁹

Study MB130045 was a randomized, double-blind, placebo-controlled, parallel-group, multiple-dose study conducted in participants with biopsy-confirmed NASH who had stage 1-3 fibrosis according to the NASH Clinical Research Network (CRN) scoring system. In this study, participants self-administered BMS-986036 or placebo, SC, for 16 weeks according to one of the following dosing regimens: BMS-986036 (10 mg QD), BMS-986036 (20 mg QW), placebo (QD). A total of 50 participants received at least 1 dose of BMS-986036 in the study.²⁰ Treatment with BMS-986036 for 16 weeks resulted in statistically significant reductions in hepatic fat fraction (as measured by magnetic resonance imaging [MRI]), decreases in ALT and aspartate aminotransferase (AST) (markers of liver injury), increases in adiponectin, and improvements in lipid profiles. Importantly, treatment with BMS-986036 was associated with improvement in fibrosis, as determined by decreases in magnetic resonance elastography (MRE) (an assessment of liver stiffness) and decreases in serum PRO-C3. In particular, BMS-986036 treatment was associated with an increase in the proportion of patients with at least a 15% decrease in MRE-assessed liver stiffness, a reduction that has been previously associated with an improvement in liver fibrosis, as observed on liver biopsy.²¹

Refer to the IB for details on these studies.

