Given that only modestly higher PD responses were observed with 10 mg QD dosing relative to the 20 mg QW dose in Study MB130-045, and the consideration that a once-weekly SC dosing regimen is likely to be more acceptable to participants than a daily dosing regimen and therefore be associated with better compliance, 3 weekly doses were identified -i.e., 10 mg, 20 mg, and 40 mg QW, that are expected to achieve clinically meaningful responses for key biomarkers of NASH, and can be administered in up to 2 injections. Model-predicted percent change from Baseline in key biomarkers for typical NASH study participants are noted in [Table 4](#) below.

Table 4 Model-Predicted Percent Change from Baseline in Key Biomarkers for Typical Participants with NASH

Biomarker	Model-predicted typical % change in response at trough concentrations with various QW doses of BMS-986036		
	10 mg QW	20 mg QW	40 mg QW
Hepatic fat content	-24.8	-29.7	-31.9
Alanine aminotransferase	-16.7	-22.6	-26.7
PRO-C3	-7.0	-12.4	-17.4
Adiponectin	11.4	18.3	24.0

NASH = nonalcoholic steatohepatitis; PRO-C3 = N-terminal type 3 collagen propeptide; QW = once weekly

The safety and PK of 20 mg QW and 40 mg QW dosing regimens for 3 weekly doses has been recently characterized in a Phase 1 study in obese healthy Japanese participants. Preliminary results show that exposure is generally dose proportional between 20 mg and 40 mg QW, and the 40 mg QW dose was safe and well tolerated (refer to IB for additional details). The 40 mg QW dose is hypothesized to provide increased efficacy compared to that of the 20 mg QW dose, but with lower overall BMS-986036 exposure than that of the 10 mg QD dose. Additionally, compared to 10 mg QD, the 40 mg QW dose is expected to provide a higher margin relative to the exposure associated with nonclinical bone-related AEs, and it also provides a lower burden of PEG. Evaluation of the 10 mg QW and 40 mg QW dose regimens is expected to facilitate a more complete evaluation of the dose-response profile of BMS-986036.

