Any pregnancy that occurs in a female partner of a male study participant should be reported to sponsor or designee during at least 5 half-lives after product administration (5 days) plus 30 days (duration of ovulatory cycle) for a total of 35 days after the end of the Double-Blind Treatment Period. In order for the sponsor or designee to collect any pregnancy surveillance information from the female partner, the female partner must sign an ICF for disclosure of this information. Information on this pregnancy will be collected on the Pregnancy Surveillance Form.

Laboratory Test Result Abnormalities

The following laboratory test result abnormalities should be captured on the nonserious AE eCRF page or SAE eCRF page, as appropriate. Paper forms are to be used only in the event that the electronic system is not functioning.

- Any laboratory test result that is clinically significant or meets the definition of an SAE
- Any laboratory test result abnormality that required the participant to have study medication discontinued or interrupted
- Any laboratory test result abnormality that required the participant to receive specific corrective therapy

It is expected that wherever possible, the clinical rather than laboratory term would be used by the reporting investigator (e.g., anemia versus low hemoglobin value).

Potential Drug-Induced Liver Injury

Wherever possible, timely confirmation of initial liver-related laboratory abnormalities should occur prior to the reporting of a potential DILI event. All occurrences of potential DILIs, meeting the defined criteria, must be reported as SAEs (see Appendix 8 for reporting details). **Repeat laboratory testing may be performed locally**, and the results should be promptly communicated to the investigator site.

For the purpose of evaluating a potential DILI, the Baseline value is defined as the mean of the test results from analysis of samples collected during Screening and on Day 1.

Note that the evaluation processes below do not replace SAE reporting per defined criteria in [Appendix 8](#).

Evaluation of Participants with New Elevations of Aminotransferases and/or Total Bilirubin

Repeat laboratory testing (including ALT, AST, fractionated bilirubin and alkaline phosphatase) and physical examination should be performed within 48-72 hours when:

- Participants with normal Baseline aminotransferase (ALT and/or AST) values develop elevations greater than $3\times$ the ULN based upon the central lab, or

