6.2.4 Clinical Laboratory Parameters

Based on the safety population, continuous laboratory results will be summarized by visit, treatment group, and pooled BMS-986036. Categorical results such as those for urinalysis will be summarized by number and percentage of participants in each category. These summaries will be based on central laboratory results, except in rare circumstances in which only a local lab value is available then a local lab value may be used. This value will be presented in the same unit and summarized with the central results from other participants. Summaries will present both actual and change-from-baseline results for continuous values.

Sponsor: Bristol-Myers Squibb

Protocol no: MB130-068

The participants with abnormal post-baseline values of laboratory parameters (with available threshold values) will be descriptively summarized by counts and percentages by time point.

Laboratory values below the lower limit or above the upper limit of quantification will be imputed to the lower or upper limit, respectively, for summary tables. The actual values will be displayed in the listings.

Box plots will be presented by time point. All laboratory data specified in the summary tables will be present in listings.

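### SAP 4.3.5 counts transaminase elevations only in multiples of ULN, which tilts the >3x ULN comparison between arms in favour of active drug

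*SAP*

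**What the plan says.** **The counts.** SAP 4.3.5, under "Potential hepatotoxicity by time point", lists "Aspartate aminotransferase (AST) or alanine aminotransferase (ALT) > 3 x upper limit of normal (ULN) or > 5 x ULN", total bilirubin above 2x ULN, and the combination of transaminase above 3x ULN with bilirubin above 2x ULN. SAP 6.2.4 adds that participants with values beyond a threshold "will be descriptively summarized by counts and percentages by time point". Neither section gives a multiple of baseline, a shift from baseline category or a worst post-baseline count.

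**Who can enter.** Protocol 8.3.2 excludes ALT and AST only above 5 times "the upper limit of normal (ULN) as defined by the central laboratory".

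**What the drug is expected to do.** Protocol 6.2.2, Table 4 ("Model-predicted typical % change in response at trough concentrations with various QW doses of BMS-986036") gives ALT changes of -16.7%, -22.6% and -26.7% at 10, 20 and 40 mg. It does not model AST. Protocol 6.1.2 reports falls in both enzymes in the earlier NASH study, without a size.

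**The protocol's own liver criteria.** Protocol 8.5.3.1 states: "For the purpose of evaluating a potential DILI, the Baseline value is defined as the mean of the test results" from Screening and Day 1. The first scenario in its interruption criterion combines a transaminase above 2x Baseline and above 3x ULN with a bilirubin, INR or symptom criterion. The SAP tabulates none of this, and its general baseline (SAP 8.1) is the last pre-dose value. Other protocol criteria are ULN-based, including the definition of potential DILI in Appendix 8.

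**The concern.** A count above 3x ULN reads naturally as a count of treatment-emergent liver signals only if few participants start above the line and treatment does not move people across it. Neither condition is secured here. Someone who enters at 3.5x ULN and never changes counts as potential hepatotoxicity at each visit on placebo. At 40 mg the same person is expected to fall to 3.5 x 0.733 = 2.57x ULN and drop out of the count. Randomisation balances the baselines but not this, because the drug itself shifts the on-treatment distribution.

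At stake is the between-arm reading of the main hepatotoxicity table. It could show active drug at or below placebo while a small number of participants on active drug have real rises. Protocol 6.2.1 says that Phase 3 design and dose selection will draw on this study's safety results.

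**Working it through.** The plan states no figure for this point, so there is nothing to reproduce. The check has two parts.

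**1. Arithmetic from the documents' figures**

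Let b be baseline ALT in multiples of ULN and r the predicted fractional fall. The expected on-treatment level is b(1 - r).

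- Baseline below which the expected level is under 3x ULN: 3/(1 - r), which is 3.00 on placebo (assuming no change), 3.60 at 10 mg, 3.88 at 20 mg and 4.09 at 40 mg. Baselines from 3 up to these values leave the count on drug and stay in it on placebo.
- Rise from the on-treatment level needed to exceed 3x ULN: 3/[b(1 - r)]. At b = 1.5 this is 2.00-fold on placebo and 2.73-fold at 40 mg. The ratio 1/(1 - r) is 1.20, 1.29 and 1.36 at the three doses.
- Example: a 2.5-fold rise from b = 1.5 gives 1.5 x 2.5 = 3.75x ULN on placebo (counted) and 1.5 x 0.733 x 2.5 = 2.75x ULN at 40 mg (not counted).
- Mean change does not replace a count. That 40 mg case moves the mean of 49 participants by (2.75 - 1.10)/49 = 0.03x ULN, against an expected fall of 1.5 x 0.267 = 0.40x ULN.

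**2. Size under assumptions**

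The documents give no baseline ALT distribution, placebo change or within-person variability. Assumed here: log-normal baseline truncated at 5x ULN, no placebo change, multiplicative within-person error, one visit, and 4% of the 40 mg arm with ALT at 3x their unreduced baseline. The 40 mg count is 0.96 x P(uninjured exceeds) + 0.04 x P(injured exceeds). For median 1.5, log-SD 0.6 and within-person log-SD 0.25:

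- >3x ULN, no injury: placebo 12.4%, 40 mg 4.2%.
- >3x ULN, with injury at 40 mg: 0.96 x 4.2 + 0.04 x 72.7 = 6.9%.
- >2x Baseline and >3x ULN, with injury: placebo 0.15%, 40 mg 0.04 x 70.6 = 2.8%.

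With 49 per arm, 12.4% is about 6 people, 6.9% is 3 to 4, and the injured 4% are about 2.

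| Median (x ULN) | log-SD | Within-person log-SD | Placebo >3x ULN | 40 mg >3x ULN, 4% injured |
|---|---|---|---|---|
| 1.0 | 0.5 | 0.2 | 2.0% | 2.4% |
| 1.0 | 0.6 | 0.25 | 4.2% | 3.1% |
| 1.3 | 0.6 | 0.25 | 8.8% | 5.3% |
| 1.5 | 0.6 | 0.25 | 12.4% | 6.9% |
| 1.8 | 0.6 | 0.25 | 18.0% | 9.5% |

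The >5x ULN count is much less affected, because values above 5x ULN are excluded at entry. Placebo against 40 mg with injury is 1.0% v 1.5% at median 1.3, 1.5% v 1.8% at 1.5 and 2.5% v 2.4% at 1.8 (log-SD 0.6 throughout).

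**If injury instead multiplies the drug-lowered ALT** (median 1.5, log-SD 0.6), the 40 mg figures are smaller:

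- >3x ULN: 0.96 x 4.2 + 0.04 x 54.5 = 6.2%, against 12.4% on placebo.
- >2x Baseline and >3x ULN: 0.04 x 41.5 = 1.7%, against 0.15%.

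**The case against.** The strongest reply has four parts.

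**Other outputs exist.** SAP 4.3.5 and 4.5 include change from baseline by visit. SAP 6.2.1 and 6.2.2 tabulate AEs and SAEs and plan a DILI graph, and SAP 6.2.4 plans box plots and listings. Potential DILI must be reported as an SAE, and laboratory abnormalities that lead to interruption or discontinuation are recorded as AEs. The bilirubin count does not depend on ALT. This stands. A reader might infer that real liver injury on active drug would be hidden; the documents do not support that. What remains is that none of these outputs gives an undistorted transaminase count by arm. The DILI graph's axes are not specified, and the table shells are in a separate document.

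**The baseline-relative count finds no new cases.** Anyone above 2x Baseline and above 3x ULN is already in the >3x ULN count. This is correct. That count removes background; it does not uncover missed cases. It also leaves unequal sensitivity: exceeding 2x Baseline takes a 2.00-fold rise on placebo and 2/0.733 = 2.73-fold at 40 mg.

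**The protocol does not judge liver safety solely against Baseline.** This is also correct. Appendix 8 and several 8.5.3.1 criteria use ULN, and the SAP thresholds match Appendix 8. Nor does the protocol have a stand-alone category of above 2x Baseline and above 3x ULN; an accompanying criterion is always required.

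**The size is assumed.** This stands, and Table 4 models ALT only, while the SAP count is of AST or ALT.

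**Conclusion.** The point holds for the >3x ULN comparison between arms. Its direction follows from the documents: entry up to 5x ULN, a predicted ALT fall of 17% to 27%, and counts made only against ULN. The two features act differently. The entry ceiling creates counts without injury, which persist mostly on placebo; the ALT fall raises the rise needed for a true case to be counted on active drug.

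The size cannot be fixed from the documents. Across the settings examined, with injury at 3x unreduced baseline, the effect runs from dilution (2.0% v 2.4%) to clear reversal (18.0% v 9.5%). It assumes no placebo change and ALT behaving as in Table 4. The >5x ULN count is a partial safeguard.

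This is a descriptive safety table in a Phase 2 study, and no efficacy conclusion changes. It is a worthwhile low-cost improvement, not evidence that a safety signal would go unseen.

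**What to change.** In SAP 4.3.5, with matching text in 6.2.4, add:

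1. A shift table for ALT and for AST, by arm, from baseline ULN category to worst post-baseline ULN category. State whether unscheduled values enter it: SAP 8.1 otherwise excludes them from summaries, which could drop the 48-72 hour liver retests.
2. A count by arm of ALT or AST above 2x Baseline and above 3x ULN, alone and with the protocol's accompanying bilirubin, INR and symptom criteria. Label the stand-alone version as an analysis category derived from the transaminase part of the interruption criterion, not as a protocol rule.
3. A statement that these tables use the protocol's DILI Baseline (mean of Screening and Day 1).
4. A count by arm relative to the participant's own on-treatment nadir, with the multiple prespecified. This alone asks for the same proportional rise in every arm. Show it without a ULN floor, since a floor would bring the inequality back.

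Keep the existing ULN counts. The cost is one or two additional descriptive tables from data already collected. No monitoring, interruption or stopping rule changes.
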